2.4.3 Prior, concomitant or post-treatment medications

The prior, concomitant and post-treatment medications will be presented for the safety population by category (all drugs, LMT). For CV drugs, the concomitant medications will be presented.

Medications will be summarized by treatment group according to the WHO-DD dictionary, considering the first digit of the anatomic therapeutic chemical (ATC) category class (anatomic category) and the first 3 digits of the ATC class (therapeutic category). All ATC codes corresponding to a medication will be summarized, and patients will be counted once in each ATC category (anatomic or therapeutic) linked to the medication. Therefore patients may be counted several times for the same medication.

The table for all prior medications will be sorted by decreasing frequency of ATCs based on the overall incidence across treatment groups. In case of equal frequency, alphabetical order will be used.

The tables for all concomitant and post-treatment medications will be sorted by decreasing frequency of ATC followed by all other therapeutic classes based on the incidence in the

alirocumab treatment group. In case of equal frequency regarding ATCs, alphabetical order will be used.

Concomitant CV drugs will be summarized by chemical class and standardized medication name and by therapeutic class and standardized medication name. Tables will be sorted by decreasing frequency of chemical or therapeutic classes and then of standardized medications within each class based on the incidence in the alirocumab treatment group.

Lipid modifying therapies (statins and other LMTs, including nutraceutical products that may affect lipids) will be summarized by pre-specified categories and standardized medication name. The table for prior LMTs will be sorted by decreasing frequency of standardized medication incidence in the overall treatment group within categories. The tables for concomitant and post-treatment LMTs will be sorted by decreasing frequency of standardized medication incidence in the alirocumab treatment group.

In addition, background LMT use at randomization will be summarized by treatment group and overall using the following categories:

- Proportion of patients with any statin
- Proportion of patients with statin alone
- Proportion of patients with any statin in addition to other LMT
- Proportion of patients with other LMT only (without statin)
- Proportion of patients with any LMT other than statins:
 - Fibrates
 - Bile acid sequestrants
 - Cholesterol absorption inhibitor
 - Nicotinic acid and derivates
 - Omega 3 fatty acids ≥ 1000 mg/day
 - PCSK9 inhibitor
 - Nutraceuticals impacting lipids
 - Other
- Proportion of patients with no LMT (neither statin or other LMT)
- The statin therapies will also be presented according to intensity (high intensity, moderate intensity, low intensity) according to the below table (3):

High-intensity statin therapy	Moderate-intensity statin therapy	Low-intensity statin therapy
Daily dose lowers LDL-C on average by approximately $\geq 50\%$	Daily dose lowers LDL-C on average by approximately 30 to $<50\%$	Daily dose lowers LDL-C on average by $<30\%$
Atorvastatin 40–80 mg	Atorvastatin 10–20 mg	Simvastatin 10 mg
Rosuvastatin 20–40 mg	Rosuvastatin 5–10 mg	Pravastatin 10–20 mg
	Simvastatin 20–40 mg	Lovastatin 20 mg
	Pravastatin 40–80 mg	Fluvastatin 20–40 mg
	Lovastatin 40 mg	Pitavastatin 1 mg
	Fluvastatin XL 80 mg	
	Fluvastatin 40 mg BID	
	Pitavastatin 2–4 mg	

Regarding doses not included in this table:

- A statin dose that falls in between two intensity classes will be counted in the class of lowest intensity (ie, pravastatin 30 mg will be counted as low intensity, atorvastatin 30 mg will be counted as moderate intensity).
- A statin dose under the lower threshold of low intensity will be counted as low intensity (ie, lovavastatin 10 mg will be counted as low intensity).
- A statin dose above the higher threshold of high intensity will be counted as high intensity (ie, rosuvastatin 80 mg will be counted as high intensity).
- Simvastatin ≥ 80 mg will be counted as high intensity, while simvastatin <80 mg and ≥ 20 mg will be counted as moderate intensity.
- Statin therapy will also be reported by type and dose

As well, glucose lowering treatment (insulin and others) use at baseline, Week 12 and Week 24 will be summarized by treatment group, categories and standardized medication name. Pre-specified categories are:

- Insulins
 - Fast acting
 - Intermediate (excluding premix)
 - Premixed
 - Long acting
 - Inhaled
- Other glucose lowering treatments
 - Biguanides
 - Sulfonylureas
 - Sulfonamides
 - Alpha glucosidase inhibitors
 - Thiazolidinediones

- DPP-4 inhibitors
- SGLT2 inhibitors
- GLP-1 receptor agonists
- Other blood glucose lowering drugs, if applicable (excluding SGLT2 inhibitors and GLP-1 receptor agonists)

Tables will be sorted by decreasing frequency of standardized medication incidence within categories in the overall treatment group at baseline and in the alirocumab treatment group at Week 12 and Week 24.

The number of glucose lowering treatments will be described by treatment arm (See [Section 2.1.9](#)).

2.4.4 Extent of investigational medicinal product exposure and compliance

The extent of IMP exposure and compliance will be assessed and summarized by actual treatment within the safety population ([Section 2.3.2](#)).

The extent of IMP exposure will be assessed by the total number of injections by patient and the duration of IMP injection exposure in weeks is defined as: (date of last dose of double-blind IMP injection + 14 days – date of first dose of double-blind IMP injection) / 7, regardless of unplanned intermittent discontinuations (see [Section 2.5.3](#) for calculation in case of missing or incomplete data). Parameters will be summarized as quantitative variables using number, mean, SD, median, Q1, Q3, minimum, and maximum (non-integer values will be rounded to 1 decimal place). In addition, the durations of exposure will be summarized and presented graphically using bar chart displaying the percentage of patients according to the following categories: ≥ 1 day to <4 weeks, ≥ 4 weeks to <8 weeks, ≥ 8 weeks to <12 weeks, ≥ 12 weeks to <16 weeks, ≥ 16 weeks and <24 weeks and ≥ 24 weeks. Non-integer values will be rounded to 1 decimal place.

2.4.4.1 Titration

The number and percentage of patients with an up-titration in the alirocumab group will be described. Patients with an up-titration are defined as up-titrated patients according to IVRS/IWRS Week 12 transaction with at least 1 injection of alirocumab 150 mg afterwards.

2.4.4.2 Compliance

A given administration will be considered noncompliant if the patient did not take the planned dose of treatment as required by the protocol. No imputation will be made for patients with missing or incomplete data.

Compliance will be assessed using the following parameters:

- The mean injection frequency will be defined for each patient as the average number of days between 2 injections, that is: (last injection date – first injection date) / (number of injections - 1) for patients receiving at least 2 injections.

- The overall compliance for injections will be defined for each patient as: $100 - (\text{number of injections performed during the study period} / \text{number of theoretical injections to be performed during the study period})$, considering that injections should be performed every two weeks (+/- 3 days as per protocol).
 - Number of theoretical injections will be defined for each patient as: $[(\text{last injection date} - \text{first injection date}) / 14] + 1$

These parameters will be summarized descriptively (N, mean, SD, median, Q1, Q3, minimum, and maximum).

- Percentage of patients with overall compliance <80% and $\geq 80\%$ will be presented
 - Percentage of patients who discontinued temporarily in relation with an AE, will be described and for these patients, the number of injections not performed per patient will be presented by category: 1 injection, 2 injections, 3 or more injections.

Cases of symptomatic overdose with IMP (ie, an event that is suspected by the Investigator or spontaneously notified by the patient (not based on systematic injection counts), and defined as at least twice of the intended dose within the intended therapeutic interval (ie, 2 or more injections are administered in <7 calendar days)) will be specified as an AESI and will be listed and described as such in the AE analysis ([Section 2.1.4.1](#)).

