8 STUDY TREATMENTS

8.1 INVESTIGATIONAL MEDICINAL PRODUCT(S)

Sterile alirocumab drug product will be supplied at a concentration of 75 mg/mL and 150 mg/mL in an aqueous buffer, pH 6.0, containing sucrose, histidine, and polysorbate 20, both as 1 mL volume, in an auto-injector (also known as prefilled pen).

Sterile placebo for alirocumab will be prepared in the same formulation as alirocumab without the addition of protein as 1 mL volume in a prefilled pen, for the patients to perform injection training, as well as for those in the placebo treatment arm.

During the screening period, the patient (or another designated person) will have to perform a placebo self-injection training, using a prefilled pen, before the first administration of IMP.

For those patients randomized to alirocumab, the initial dose is 75 mg administered subcutaneously once Q2W. The dose will be increased in a blinded fashion to 150 mg Q2W at Week 12 for patients randomized to alirocumab if the Week 8 LDL-C value is ≥ 70 mg/dL (1.81 mmol/L).

Those patients randomized to placebo will be administered their injection subcutaneously Q2W throughout the duration of the 24-week treatment period.

NOTE: in order to ensure the continuity of the study treatment without interruption (only in the event the manufacturer faces any performance or supply issues of the prefilled pen), contingency alternatives are:

- in case of disruption of the 150 mg prefilled pen only, if the use of 75 mg prefilled pens is maintained, patients will need to administer 2 injections as follows:
 - 2 injections of 75 mg as 1 mL each in a prefilled pen for patients receiving the 150 mg dose
 - 1 injection of 75 mg as 1 mL in a prefilled pen plus 1 injection of placebo as 1 mL in a prefilled pen for patients receiving the 75 mg dose
 - 2 placebo injections as 1 mL each in a prefilled pen for patients receiving placebo

OR

- in case of disruption of either 75 mg or 150 mg or both prefilled pens, patients will be switched to the use of prefilled syringes of placebo, 75 mg and 150 mg, with one injection of 1 mL for each of these doses

Should this occur, the alternative IMP will be maintained until the end of the study.

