8.1.2 Timing of administration

During the screening period, patients or the designated person will have to perform a placebo self-injection training using a prefilled pen, before the first IMP injection.

At the randomization visit, the first IMP injection will be done at the site by the patient or another designated person (such as spouse, relative, etc) under direct site staff supervision. Patients will be monitored at the investigational site for at least 30 minutes after this first injection in this study. If the designated person changes during the course of the study, the new designated person will need to be trained with placebo.

IMP subcutaneous injections will then be performed outside of the clinic, Q2W up to the last injection. If the injection is scheduled to take place on the same date as the site visit, then the IMP should be administered after the blood sampling has been completed. In exceptional cases, if a patient prefers to have the injection performed at the study site and provisions are able to be made to accommodate the administration of injections at the site, it may also be allowed.

IMP should be administered subcutaneously Q2W, ideally at approximately the same time of the day; however, it is acceptable to have a window period of ± 3 days. The time of the day is based upon the patient's preference.

If by mistake or due to other circumstances an injection is delayed by:

- more than 7 days from the missed date or completely missed, then the patient should return to the original schedule of IMP administration without administering delayed injections.
- less than or equal to 7 days from the missed date, then the patient should administer the delayed injection and then resume the original schedule of IMP administration.

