11.4.1 Extent of study treatment exposure and compliance

The extent of study treatment exposure and compliance will be assessed and summarized by actual treatment received within the safety population.

In order to ensure the continuity of the investigational treatment for the patients without interruption (only in case a disruption occurs in the availability of device components or during production of the prefilled pen), back-up plans may be implemented as described in [Section 8.1](#). In that case, exposure to initial device and back-up device will be summarized and impact on study results will be assessed. More details will be provided in the SAP, if applicable.

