11.4.1.2 Compliance

A given administration will be considered noncompliant if the patient did not take the planned dose of treatment as required by the protocol. No imputation will be made for patients with missing or incomplete data.

Compliance will be assessed using the following parameters:

- The injection frequency will be defined for each patient as the average number of days between 2 injections, that is: (last dose date – first dose date)/(number of injections -1).

This parameter will be summarized descriptively (N, Mean, SD, Median, Min and Max).

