1.5 MODIFICATIONS TO THE STATISTICAL SECTION OF THE PROTOCOL

Definition of screened patients

In protocol section 11.2, screened patients are defined as any patient who met the inclusion criteria and signed the informed consent. In SAP version 4.0 and above, definition of screened patients was updated to any patients who signed the informed consent only.

Definition of an additional compliance parameter

The overall compliance was added in assessment of extent of investigational medicinal product exposure and compliance.

Additional effects added to the analysis model of the primary efficacy endpoint

Additional effects were added to the analysis model of the primary efficacy endpoint initially defined in protocol section 11.4.2.1: the strata (ie, diabetes type), the strata-by-time point interaction, and the treatment-by-strata-by-time point interaction.

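### SAP 2.4.4.2, as it reads in the available text, defines overall compliance as 100 minus a ratio, which is not a usable compliance percentage; check the operator against the source

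*SAP*

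**What the plan says.** SAP section 2.4.4.2 (Compliance) introduces the parameter with "The overall compliance for injections will be defined for each patient as: $100". The dollar sign is typesetting mark-up from the conversion. A minus sign follows, then a bracket holding injections performed divided by theoretical injections.

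The denominator is introduced by "Number of theoretical injections will be defined for each patient as". It equals the days from first to last injection divided by 14, plus 1.

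The section asks for the usual summary statistics of this parameter and then a two-row table, "Percentage of patients with overall compliance <80% and" 80% or above. Under SAP 2.4.4 these outputs are by actual treatment in the safety population.

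No other place gives a second formula. SAP 1.5 records only that "The overall compliance was added in assessment of extent of investigational medicinal product exposure and compliance". Protocol 11.4.1.2 has a single parameter: "The injection frequency will be defined for each patient as the average number of days between 2 injections".

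**The concern.** A compliance percentage should be 100 for a patient who takes every planned injection, and should fall as injections are missed. The expression in 2.4.4.2 does neither, whether the bracket is taken as a plain ratio or as a percentage.

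Missed injections in the middle of a course are foreseen. Protocol 8.1.2 says that after a delay of more than 7 days, "then the patient should return to the original schedule of IMP administration without administering delayed injections". The parameter therefore has real variation to describe, and the 80% split was specified in advance to describe it.

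If the line is programmed as it reads, the table could show all patients as compliant or almost none, depending on how the programmer treats the bracket. The mean and quartiles would run in the wrong direction. A silent correction by the programmer would give a sensible table but would be an undocumented departure from the SAP.

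**Working it through.** The documents state no compliance figure to reproduce, so the check evaluates the formula directly.

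**Inputs**
- Last planned injection at Week 22 (Protocol synopsis), that is 22 × 7 = 154 days after the first.
- Theoretical injections (SAP 2.4.4.2): 154/14 + 1 = 12.
- Dosing window of ±3 days (Protocol 8.1.2; SAP 2.4.4.2).
- Six pens per kit (Protocol 8.5), with kits allocated at Week 0 and Week 12 (Protocol 8.4): 12 scheduled pens.

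**Scores for a patient whose first and last injections are 154 days apart, with n injections performed**

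| n of 12 | As it reads: 100 − n/12 | Bracket as percentage: 100 − 100 × n/12 | 100 × n/12 | Mean days between injections: 154/(n − 1) |
|---|---|---|---|---|
| 12 | 99.00 | 0 | 100 | 14.0 |
| 11 | 99.08 | 8.3 | 91.7 | 15.4 |
| 10 | 99.17 | 16.7 | 83.3 | 17.1 |
| 9 | 99.25 | 25.0 | 75.0 | 19.25 |
| 6 | 99.50 | 50.0 | 50.0 | 30.8 |
| 2 | 99.83 | 83.3 | 16.7 | 154 |

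**Literal reading.** The whole range from full adherence to first-and-last-only spans 99.83 − 99.00 = 0.83 points, in the wrong direction. A score below 80 needs a ratio above 20, or more than 20 × 12 = 240 injections. Two extremes show how far off that is:
- Twelve injections all 8 days apart (14 − 3 − 3) span 88 days. Theoretical = 88/14 + 1 = 7.29, the ratio is 1.647 and the score is 98.35.
- All 12 scheduled pens on one day give theoretical = 1 and a score of 100 − 12 = 88.

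The below-80% row is empty for any plausible patient.

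**Percentage reading.** A score of 80 or more needs a ratio of 0.2 or less, that is at most 2 of 12 injections (0.2 × 12 = 2.4). Nearly everyone falls below 80%, and a fully adherent patient scores 0.

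**Multiplication.** With 100 × ratio both rows can be filled, and the cut falls between 10 and 9 of 12. A last injection 3 days early or late does not move it:
- Theoretical becomes 151/14 + 1 = 11.79 or 157/14 + 1 = 12.21.
- Ten injections score 84.8% or 81.9%.
- Nine injections score 76.4% or 73.7%.

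The last column of the table shows that the separate injection-frequency parameter still moves the right way.

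**The case against.** The strongest objection is that the point rests on one character in a formula that passed through PDF conversion, so the sponsor's document may show a multiplication sign. That possibility stands and cannot be excluded here. Two features of the text make a real minus sign more likely:
- Multiplication signs survive elsewhere in the same SAP: the primary endpoint formula in 2.1.3.1, the liver thresholds in 2.4.6.3, and the HbA1c conversion in 2.5.1, which holds a multiplication and a minus together.
- SAP section 3 mentions compliance with capsules and days of under- or above-planned dosing, although the study drug is only injected. This suggests compliance text carried over from elsewhere.

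Neither is proof.

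It is also fair to say that the intent is obvious, and that fully adherent patients scoring 99 or 0 would probably be noticed at first output. That lowers the likely harm, but the SAP still gives no correct formula.

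A reader might infer more than the documents support:
- *That the table is bound to show every patient at 80% or above.* This follows only from the literal reading. The percentage reading gives nearly the opposite table.
- *That the formula is faulty because doses lost after permanent discontinuation do not count.* The theoretical count ends at the patient's own last injection whichever operator is used. That is a legitimate on-treatment definition. Discontinuation is reported in SAP 2.2 and exposure in SAP 2.4.4.
- *That a counting rule is needed because, in one supply contingency, "patients will need to administer 2 injections as follows".* Nothing shows that the contingency was used. Protocol 11.4.1 says that in that case "exposure to initial device and back-up device will be summarized and impact on study results will be assessed", and leaves the details to the SAP if applicable. That is a separate matter from the operator.

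**Conclusion.** On the available text the formula is wrong under both readings of the bracket, and no other passage corrects it. The two-row table and the summary statistics of this one parameter would be uninformative or inverted.

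Severity is low. The parameter is descriptive and was added in the SAP. A reader might suspect an effect on the on-treatment results, but the modified intent-to-treat population depends on having taken at least one dose or part of one and on available LDL-C values, not on this score. No efficacy test, population or estimand uses it. Mean injection frequency, injection counts, exposure duration and the discontinuation curves are unaffected.

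The conclusion assumes that the minus sign is in the source SAP; if it is not, the point falls away. The worked scores assume a first-to-last span of 154 days and hence 12 theoretical injections.

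**What to change.** Check the operator in section 2.4.4.2 of the source SAP. If it is a minus sign, define overall compliance as 100 × (number of injections performed / number of theoretical injections), keeping the present denominator and the 80% cut. This takes one line of SAP text and one line of code; no other analysis changes. If the source already shows multiplication, nothing needs to be done.

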2.4.5 Analyses of efficacy endpoints

For statistics where international and conventional units do not impact the results (eg, means and least square (LS) means for percent changes from baseline, p-values for both percent and absolute changes from baseline, rates of patients below a threshold), derivations will be done and statistical models will be run using conventional units. For other statistics (eg, descriptive statistics at baseline and over time, absolute changes from baseline), derivations will be done with both international and conventional units.

2.4.5.1 Analysis of primary efficacy endpoint(s)

2.4.5.1.1 Primary efficacy analysis

Separate analyses will be performed for Type 1 diabetes patients on one hand (alpha risk = 0.05) and Type 2 diabetes patients on the other hand (alpha risk = 0.05), as well as in the pool population (alpha risk = 0.05). All outputs described below will be first described separately on the Type 1 diabetes patients and on the Type 2 diabetes patients, and then on the pooled data.

The percent change in calculated LDL-C from baseline to Week 24 as defined in [Section 2.1.3.1](#) will be analyzed in the ITT population using a mixed effect model with repeated measures (MMRM) approach. All post-baseline data available within Week 8 to Week 24 analysis windows will be used and missing data are accounted for by the MMRM model. The model for assessing the treatment effect in the pooled data will include the fixed categorical effects of treatment group (alirocumab versus placebo), randomization strata (ie, diabetes type, as per IVRS), time point (Week 8, Week 12, Week 20 and Week 24), treatment group-by-time point interaction, and strata-

by time point interaction, as well as the continuous fixed covariates of baseline calculated LDL-C value and baseline value-by-time point interaction. The model for assessing the treatment effect by diabetes type will include an additional interaction term: the treatment group-by-strata-by-time point interaction. The significance level (P-value) of the treatment group-by-strata interaction term at Week 24 will be also provided for this model for descriptive purpose. In case of non-convergence of the model, a model with less interaction terms will be fit.

These models will be run using SAS® Mixed procedure with an unstructured correlation matrix to model the within-patient errors. Parameters will be estimated using restricted maximum likelihood method with the Newton-Raphson algorithm. Denominator degrees of freedom will be estimated using Satterthwaite's approximation. This model will provide baseline adjusted LS means estimates at Week 24 for both treatment groups with their corresponding standard errors (SEs). To compare the alirocumab group to the placebo group, an appropriate contrast statement will be used to test the differences of these estimates, at the 2-sided 0.05 level. LS-mean difference versus placebo and the corresponding 95% confidence intervals (CIs) will be provided. Forest plot will also be provided.

Let μ_0 and μ_1 be the population means of the percent change from baseline in calculated LDL-C at Week 24 under placebo and alirocumab, respectively. The null hypothesis that will be tested in each subpopulation is:

“ $H_0 : \mu_0 = \mu_1$ ” versus “ $H_1 : \mu_0 \neq \mu_1$ ”.

The MMRM model relies on the “missing-at-random” (MAR) assumption. Sensitivity analysis with the intent to evaluate the robustness of the primary analysis using a different statistical method will be conducted (see multiple imputation model definition in [Section 2.4.5.1.3](#)). As we can never exclude the possibility for a not-missing-at-random (NMAR) missingness mechanism, sensitivity analysis to explore the impact of non-ignorable missingness on the primary efficacy analysis will be conducted (see pattern mixture model defined in [Section 2.4.5.1.3](#)).

